13 ETHICS AND REGULATORY REQUIREMENTS

This study is to be conducted in accordance with the specifications of this protocol and in accordance with principles consistent with Declaration of Helsinki, GCP, 21 CFR, ICH E6, HIPAA regulations in 45 CFR Part 164 (US only), and the Belmont Principles of respect for persons, beneficence, and justice. No protocol changes will be implemented without the prior review and approval of the IRB, except when the modification does not involve the subject's participation in the trial or where it may be necessary to eliminate an immediate hazard to a research subject. In the latter case, the change will be reported to the IRB as soon as possible, according to IRB regulations.

Additionally, the study product used in this study is manufactured, handled and stored in accordance with applicable GMP. The study product provided for this study will be used only in accordance with this protocol.

13.1 INSTITUTIONAL REVIEW BOARD/INDEPENDENT ETHICS COMMITTEE (IRB/IEC)

The Principal Investigator (PI) at the site will provide the Institutional Review Board/Independent Ethics Committee (IRB/IEC) with all appropriate materials as required by their IRB/IEC, including but not limited to the clinical study protocol, informed consent form, and any advertising materials. The study will not be initiated until the IRB/IEC provides written approval of the aforementioned documents and until approval documents have been obtained by the Principal Investigator and Sponsor or Sponsor designee. The Investigator will not participate in the decision. If the Investigator is an IRB or IEC member, documentation must be provided indicating recusal from the approval process. Appropriate reports on the progress of this study by the Principal Investigator will be made to the IRB/IEC as required by local and applicable government regulations and in agreement with policy established by the Sponsor. The Investigator is required to maintain an accurate and complete record of all written correspondence to and received from the IRB/IEC, and must agree to share all such documents and reports with the Sponsor.

No changes from the final approved protocol will be initiated without the IRB/IEC's prior written approval or favorable opinion of a written amendment, except when necessary to eliminate immediate hazards to the subjects or when the modification does not involve the subject's participation in the trial.

13.2 INVESTIGATOR'S RESPONSIBILITIES

The Investigators are responsible for performing the study in full accordance with the protocol and the current revision of the Declaration of Helsinki, the Good Clinical Practice: Consolidated

Guideline, approved by the ICH, and any applicable national and local laws and regulations. Information regarding to the study center participating in this study that cannot comply with these standards will be documented.

13.3 SUBJECT INFORMED CONSENT REQUIREMENTS

All subjects participating in this study will be given to by the Investigator and/or designee, written and oral information about the study in a language understandable by the subject. Written informed consent will be obtained from each subject prior any procedures or assessments that would not otherwise be required for the care of the subject are done and after the aims, methods, anticipated benefits, potential hazards, and insurance arrangements in force are explained and the subject has been given sufficient time to ask questions and consider participation in the study. It will also be explained to the subjects that they are free to refuse entry into the study and free to withdraw from the study at any time without prejudice to future treatment. It is permissible for a third person (e.g., a family member) to be present during the explanation of the study.

The written Informed Consent Form ICF will be in compliance with CFR 21 Part 50.27 and GCP guidelines. The Sponsor and/or designated CRO will approve the ICF and all amendments to the ICF prior to submission to the IRB/IEC. A copy of the ICF to be used will be submitted by the Investigator to the IRB/IEC for review and approval prior to the start of the study. The study site must provide the Sponsor with an unsigned copy of IRB/IEC-approved ICF along with applicable documentation to support this approval. The original signed ICF is retained in the subject's study records, and a copy is provided to the subject. A second copy may be filed in the subject's medical record, if allowed by institutional policy.

14 DATA HANDLING AND RECORD KEEPING

14.1 RECORDING AND COLLECTION OF DATA

The primary source document for this study will be the subject's medical record. If separate research records are maintained by the Investigator(s), the medical record and the research records will be considered the source documents for the purposes of auditing the study.

Applicable source data will be manually transcribed to approve case report forms (CRF). The Investigator is ultimately responsible for the accuracy of the data transcribed on the forms. All source documents and CRFs will be completed as soon as possible after the subject's visit.

The Investigator will review the CRFs to indicate that, to his/her knowledge, they are complete and accurate. Designated source documents will be signed and dated by the appropriate study personnel. The Investigator must agree to complete and maintain source documents and CRFs for each subject participating in the study.

All research data will be entered, either electronically or manually, into a computerized database. The clinical database will be designed by the clinical data manager in accordance with 21 CFR Part 11 and based on protocol requirements defined by the Sponsor in association with the Lead Investigator.

The Investigator will maintain a confidential list of study subjects that will include each subject's study number, name, date of birth, and unique hospital identification number if applicable. This list will be kept by the Investigator and will not be collected by the Sponsor. A notation will be made in the subject's case history/medical chart that he/she is participating in a clinical study and has provided a signed and dated ICF as well as a release for protected health information as required by local policies. The Investigator must also maintain a separate screening log of all the subjects screened for participation in the study; it should include gender, age, eligibility status, reason for ineligibility, if applicable; and study allocated subject number, if applicable.

14.2 CLINICAL DATA MANAGEMENT

The Sponsor and/or designated CRO will be responsible for the processing and quality control of the data. Data management will be carried out as described in the Sponsor's or CRO's standard operating procedures (SOPs) for clinical studies.

The handling of data, including data quality control, will comply with regulatory guidelines (e.g., ICH E6 GCP, and local regulations where applicable) and the Sponsor's or the CRO's SOPs as well as provisions of the study-specific Data Management Plan.

14.3 ARCHIVING

All study documentation at the Investigator site and Sponsor site will be archived in accordance with ICH GCP E6 and the Sponsor's quality standards and SOPs.

The Investigator will maintain all research records, reports, and case history reports for a period of two (2) years after regulatory approval of the investigational product. If no application is filed or if the application is not approved, records must be maintained for two (2) years after all investigations have been completed, terminated or discontinued and the FDA has been notified.

These documents should be retained for a longer period however, if required by the applicable regulatory requirements or if needed by Sponsor or its authorized representative (as per GCP 5.5.11).

At the completion of the study, details of the archival process must be provided to the Sponsor. Study records are subject to inspection by applicable health and regulatory agencies at any time.

Records to be retained by the Investigator include, but are not restricted to:

- Source data and the primary records upon which they are based (e.g., subject's progress notes, adverse event data, test results, and any other diagnostic procedures required to evaluate the progress of the study)
- Completed CRFs
- Signed protocols and protocol amendments
- Laboratory results, ranges, and certifications
- IP and accountability records
- Study personnel signature log
- Monitoring logs
- Correspondence to and from the Sponsor, designee and IRB
- Investigator and sub-investigator CVs
- Signed informed consent and protected health information consent forms
- Subject screening
- SAE reports
- IRB approval and re-approval letters
- Completed quality of life questionnaire
- Other documents pertaining to the conduct of the study

These documents must be maintained and kept on file by the Investigator so that the conduct of the study can be fully documented and monitored.

Study records should not be transferred from site or destroyed without prior written agreement between the Sponsor and the study Investigator. Study records are subject to inspection by applicable health and regulatory agencies at any time.

15 PUBLICATION PLAN

All information supplied by CytoDyn in connection with this study and not previously published, is considered confidential information. This information includes, but is not limited to, the Investigator's Brochure, clinical protocol, case report forms and other scientific data. Any data collected during the study are also considered confidential. This confidential information shall remain the sole property of CytoDyn, shall not be disclosed to others without the written consent of CytoDyn, and shall not be used except in the performance of this study.

It is understood by the Investigator that the Sponsor will use the information collected in this clinical trial in connection with the development of CytoDyn. Therefore, this information may be disclosed as required to other Investigators or appropriate regulatory authorities. By agreeing to participate in this clinical trial, the Investigator understands that he/she has an obligation to provide the Sponsor with complete test results and all data developed during this trial.

Publication and Disclosure: The site and Investigator agree to submit any proposed manuscript, presentation or other public disclosure regarding the study to Sponsor for review at least thirty (30) days prior to submitting such proposed manuscript to a publisher or delivering or making such presentation or other public disclosure to any third party. Within thirty (30) days of its receipt, Sponsor shall advise the site and/or Investigator, as the case may be, in writing of any information contained therein that is confidential information (other than research results included in a proposed manuscript) or that may impair Sponsor's ability to obtain patent protection. Sponsor shall have the right to require the site and/or Investigator, as applicable, to remove specifically identified confidential information (but may not require removal of research results from a proposed manuscript) and/or to delay the proposed submission or delivery of the proposed manuscript or presentation, or other public disclosure, for an additional sixty (60) days to enable Sponsor to seek patent protection. The site and Investigator shall not publish, publicly disclose, present or discuss any results of or information pertaining to the site's and Investigator's activities prior to completion of the trial, even if the multi-center trial or the study is terminated before its completion and the final clinical study report is signed off, or with respect to any endpoints or analyses other than those specified in this protocol.

17 APPENDIX

17.1 APPENDIX 1: ACCEPTABLE METHODS OF CONTRACEPTION

Barrier Methods	Intrauterine Device Methods	Hormonal Methods

• Male condom plus spermicide• Cap plus spermicide• Diaphragm plus spermicide	
• Copper T• Progesterone T• Levonorgestrel-releasing	
• Implants• Hormone shot or injection• Combined pill• Minipill• Patch

NOTE: choice of contraception should be discussed with primary treating oncologist to discuss the risks and benefits of different modalities of contraception.

17.2 APPENDIX 2: COMMON TERMINOLOGY CRITERIA FOR ADVERSE EVENTS V5.0

For complete detailed information please refer to the link below:

https://ctep.cancer.gov/protocolDevelopment/electronic_applications/docs/CTCAE_v5_Quick_Reference_8.5x11.pdf

1. INTRODUCTION

This Statistical Analysis Plan describes the planned analyses and reporting for the clinical trial protocol CD09_Basket, conducted by CytoDyn Inc. The reader of this Statistical Analysis Plan (SAP) is encouraged to review the complete protocol and amendments as this plan contains only a limited overview of protocol information. The main objectives of this plan are to provide details pertaining to statistical methodology, data conventions, and processes used for the analysis of data from this trial.

The format and content of this SAP are structured to provide sufficient detail to meet the requirements specified by the International Council on Harmonization (ICH) E9: Guidance on Statistical Principles in Clinical Trials. All work planned and presented in this Statistical Analysis Plan will follow the ethical guidelines published by the American Statistical Association (ASA).

The following documents were reviewed in preparation of this Statistical Analysis Plan:

- Final protocol Version 2.0 / 14-May_2020
- ASA Ethical Guidelines for Statistical Practice (2016)
- The Royal Statistical Society: Code of Conduct (2014)
- ICH Guidance on the Structure and Content of Clinical Study Reports (ICH E3, 1996)
- ICH Guidance on the Structure and Content of Clinical Study Reports (ICH E3(R1), 2013)
- ICH Guidance on the Statistical Principles for Clinical Trials (ICH E9, 1998)
- ICH Guidance on the Statistical Principles for Clinical Trials (ICH E9(R1), 2017)

2. PROTOCOL DESIGN

2.1 Design Overview

This is a single arm study with 30 patients of leronlimab (PRO 140) in patients with CCR5+ locally advanced or metastatic solid tumors.

Leronlimab (PRO 140) will be administered subcutaneously as weekly dose of 525 mg until disease progression or intolerable toxicity. Subjects participating in this study will be allowed to receive/continue standard-of-care chemotherapy or radiotherapy as per the dosing schedule included on the package insert.

In this study, patients will be evaluated for tumor response approximately every 3 months or according to institution's standard practice by CT, PET/CT or MRI with contrast (per treating investigator's discretion) using the same method as at baseline. Tumor measurements will be done

using RECIST v1.1.

The total study duration for each subject consists of pre-screening, screening, treatment, and follow-up periods. A study flow diagram is presented in Figure 2-1.

(1) Pre-Screening Period: A separate Informed Consent Form (ICF) will be used for the pre-screening. The pre-screening period is designed for evaluation of histologically or cytologically confirmed locally advanced or metastatic solid tumors and CCR5 positive status by Immunohistochemistry (IHC) assay. This assay will be performed in archival tissue from previous biopsy specimens. If archival tissue is not available then, fresh core or excisional biopsy will be done. If patient qualifies, then they will undergo full screening.

(2) Screening Period: Screening assessments will commence after obtaining signed informed consent, and will include review of medical and medication history, demographic information and baseline disease characteristics, eligibility evaluation, physical examination, vital signs, height and weight, concomitant medications, electrocardiogram (ECG), tumor imaging assessment (prior imaging assessment within the last 3 months of the Screening Visit is acceptable), routine serum biochemical, hematologic, urinalysis, serum pregnancy (if applicable). These assessments must be conducted within 28 days of the first treatment visit.

(3) Treatment Period: Subjects who meet the eligibility criteria will have completed following evaluations and assessments before receiving treatment: a) review of medical and medication history; b) physical examination, vital signs and documentation of ECOG performance status; c) ECG; d) routine serum biochemical, hematologic, urine pregnancy (if applicable) and urine laboratory assessments. Additionally, a blood sample will be collected prior to treatment administration for CTC and CAML analysis.

Leronlimab (PRO 140) will be administered subcutaneously weekly by a licensed medical professional at clinic site or self-administered by subjects at home.

[figure not shown]
Note: All initial leronlimab (PRO 140) SC weekly injections must be administered at clinic. The remaining study treatment injections may be self-administered by subjects at home after proper training by a healthcare professional.

Subjects will be allowed to continue weekly treatment until any one of the following occurs: progressive disease or unacceptable toxicity or withdrawal of consent.

(4) Follow-Up Period: An End of Treatment (EOT) visit will be conducted 30 (\pm 3) days after the last treatment visit (i.e., after last dose of leronlimab (PRO 140)). Additionally, follow-up will be done for survival status, by clinic visits or phone or another method of contact, every 3 months (\pm 1 month) for 2 years after treatment discontinuation or until death, whichever occurs first.

A subject is considered to have completed the study once all survival follow-up visit assessments up to 2 years after treatment discontinuation have been performed or until death, whichever occurs first.

Figure 2-1: Study Flow Diagram

2.2 Treatment Groups

Eligible subjects will receive leronlimab (PRO 140) administered weekly at a dose of 525 mg SC, starting on Week 1 and every week thereafter, until disease progression or intolerable toxicity.

2.3 Randomization and Stratification

Not Applicable.

2.4 Blinding

Not Applicable.

2.5 Time to Unblinding

Not Applicable.

2.6 Protocol Objective(s)

2.6.1 Primary Objective

The primary objective of this study is to assess anti-tumor activity of Leronlimab (PRO 140) in the treatment of patients with CCR5-positive, locally advanced or metastatic solid tumors as part of a defined treatment protocol.

2.6.2 Secondary Objectives

The secondary objectives of this study are:

- To collect further safety, tolerability and efficacy data.
- To evaluate correlative studies for better treatment selection in future validation studies.

2.7 Outcome Measures

2.7.1 Efficacy Outcome Measures

The efficacy outcome measures in this study are:

- Progression free survival (PFS) defined as time in months from the date of first study treatment to the date of disease progression or death from any cause, whichever comes first.

Note: All patients who receive at least one dose of leronlimab (PRO 140) will be included in the primary analyses of PFS. The Response Evaluation Criteria in Solid Tumors (RECIST v1.1) criteria will be used for objective tumor response assessment (when disease is measurable and non-measurable);

The time in months from start of treatment to progression or death will be measured for all patients who receive at least one dose of study drug. Patients will be followed up to 2 years after completion of treatment.

- Overall response rate (ORR, defined as Complete Response (CR) + Partial Response (PR)), and clinical benefit rate (CBR, defined as CR + PR + Stable Disease (SD)) in subjects with CCR5+ locally advanced or metastatic solid tumors treated with leronlimab (PRO 140)

Note: Overall response rate is defined as the proportion of patients who achieve an overall response of complete response or partial response in the total number of evaluable patients, assessed by RECIST v1.1. Clinical benefit rate is defined as the proportion of patients who achieve an overall response of complete response or partial response or stable disease in the total number of evaluable patients, assessed by RECIST v1.1. Imaging scans to be done approximately every 3 months or according to institution's standard practice.

- Time to new metastases (TTNM);

Note: Recorded time from baseline metastatic disease (at time of enrollment) to the time of development of new metastasis in different site. New metastases in same site will be also recorded.

- The change from baseline in circulating tumor cells (CTC) level in the peripheral blood.

Note: Reported unit of measure will be the number of CTCs/milliliter. CTCs enumeration will be performed at baseline and at the time of response assessment. Fraction of baseline positive and change from ≥ 5 CTCs will be recorded and reported.

- Overall survival defined as time in months from the date of first study treatment to the date of death;

Note: Patients will be followed from the start of treatment until 2 years post-treatment or death, whichever occurs first, and average survival time will be measured.

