7.16 SURVIVAL STATUS

Subjects will be followed up by clinic visits or phone call or another method of contact, for survival status every 3 months (± 1 month) for 2 years after treatment discontinuation or until death, whichever occurs first.

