Imaging scans to be done approximately every 3 months or according to institution's standard practice.

- Time to new metastases (TTNM);

Note: Recorded time from baseline metastatic disease (at time of enrollment) to the time of development of new metastasis in different site. New metastases in same site will be also recorded.

- The change from baseline in circulating tumor cells (CTC) level in the peripheral blood.

Note: Reported unit of measure will be the number of CTCs/milliliter. CTCs enumeration will be performed at baseline and at the time of response assessment. Fraction of baseline positive and change from ≥ 5 CTCs will be recorded and reported.

- Overall survival defined as time in months from the date of first study treatment to the date of death;

Note: Patients will be followed from the start of treatment until 2 years post-treatment or death, whichever occurs first, and average survival time will be measured.

Exploratory Outcome (Endpoints) Measures:

- Measure immune biomarkers in CTCs, metastatic tissue and immune cells such as CAML and correlate with therapeutic benefit (PFS); and
- Assess changes in CTCs and CAML after treatment and perform correlative analysis of CCR5 expression.

PFS will be calculated using Kaplan-Meier curves and the median PFS will be read from this curve. Response rates (overall response rate, clinical benefit rate) will be calculated using proportions and 95% confidence intervals. Time to new metastases and overall survival will also be analyzed using Kaplan-Meier curves. Exploratory serial blood markers will be related to PFS using Cox regression, and to response using logistic regression.

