7.10.7 Time to Overall Survival (OS)

Time to Overall Survival (OS) in months will be calculated according to the formula noted below:

$$\text{Time to Overall Survival} = (\text{Date of death due to any cause} - \text{Date of first treatment} + 1)/30.4$$

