8.2.1.5 Overall Survival

The Overall Survival will be presented and summarized descriptively.

The time to overall survival in months will be calculated using the formula in [Section 7.10.7](#) and summarized descriptively.

The likelihood score test in the Cox proportional hazards model (which is the equivalent of the Log Rank test) will be used to compare the time to overall survival between the treatment groups. Kaplan-Meier analysis will be used to depict the median time (days) to overall survival.

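### Overall survival follow-up is tied to the end of treatment: the planned average survival time is undefined and, read literally, too low, and the Kaplan-Meier curve after month 24 may be informatively censored

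*SAP*

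**What the plan says.** The time origin is first dose: SAP 2.7.1 has "Overall survival defined as time in months from the date of first study treatment to the date of death". The end of observation has a different anchor. Protocol 7.16 follows subjects "for survival status every 3 months (± 1 month) for 2 years after treatment discontinuation or until death, whichever occurs first", and SAP 2.1 repeats "for 2 years after treatment discontinuation or until death, whichever occurs first". Treatment has no fixed length: "Subjects will be allowed to continue weekly treatment until any one of the following occurs: progressive disease or unacceptable toxicity or withdrawal of consent" (SAP 2.1).

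Three OS summaries are planned or implied:

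- **Kaplan-Meier.** SAP 8.2.1.5: "Kaplan-Meier analysis will be used to depict the median time (days) to overall survival". Protocol 8.7.3: "Time to new metastases and overall survival will also be analyzed using Kaplan-Meier curves".
- **An average.** The OS note in SAP 2.7.1, also in Protocol 8.7.3: "Patients will be followed from the start of treatment until 2 years post-treatment or death, whichever occurs first, and average survival time will be measured".
- **A descriptive summary.** SAP 8.2.1.5 summarises the OS times from the formula in SAP 7.10.7. That formula starts from "Date of death due to any cause" and has no entry for a subject still alive. SAP 8 lists the arithmetic mean among the default statistics for continuous variables.

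Neither document gives an OS censoring date, a common cut-off or a horizon for the average.

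**The concern.** If follow-up ends 24 months after treatment stops, a living subject is still observed at month t > 24 only if treated for at least t − 24 months. Progression is one of the events that end treatment, so early progressors tend to leave the risk set first. Kaplan-Meier requires that subjects censored at a given time have the same later risk as those who remain, and this rule gives no assurance of that after month 24.

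The average raises a separate problem. A mean survival time needs either complete follow-up to death or a stated horizon, and the plan has neither. A programmer following SAP 7.10.7 and SAP 8 literally would average over the subjects who died. That drops everyone alive at the end of follow-up, and those are the long survivors. The result could be reported as mean survival in a single-arm study that has no control group to expose the error.

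**Working it through.** The documents state no figure on this point, so there is nothing to reproduce. They give no expected treatment duration or survival either, so all durations below are assumptions.

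**Base case.** Time on treatment T is exponential with median 6 months. Survival after stopping, P, is exponential with median 12 months and independent of T. OS = T + P, and censoring is at T + 24.

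- Mean T = 6/ln 2 = 8.66 months. Mean P = 12/ln 2 = 17.31 months. True mean OS = 25.97, or 26.0 months.
- A subject is censored by the rule if P > 24. The probability is 2^(−24/12) = 0.25.

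**Average survival time**

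- *Deaths only (literal SAP 7.10.7).* Mean of P given P ≤ 24 = [17.31 − 0.25 × (24 + 17.31)] / 0.75 = 9.31. Adding 8.66 gives 17.97, or 18.0 months, which is 8.0 too low.
- *All observed times.* Mean of min(P, 24) = 17.31 × 0.75 = 12.98. Adding 8.66 gives 21.64, or 21.6 months, which is 4.4 too low (25.97 − 21.64 = 4.33 before rounding).
- *Shared prognosis.* If one log-normal multiplier (log-SD 0.7) acts on both T and P, simulation gives a true mean of 33.2 months, against 17.3 deaths-only and 23.8 over all observed times.

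**Kaplan-Meier in the base case**

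- True survival is S(t) = 2 × 2^(−t/12) − 2^(−t/6), so S(24) = 43.75%, S(36) = 23.4% and S(48) = 12.1%. Setting S = 0.5 gives a median of 21.3 months.
- Up to month 24 the rule censors nobody, so the curve and this median are correct.
- After month 24 the at-risk set always consists of subjects whose treatment ended within the last 24 months or is still going on. The share off treatment stays at (0.4375 − 0.0625)/0.4375 = 6/7, where 0.0625 = 2^(−24/6) is the share still on treatment at month 24. In this model deaths occur only off treatment, so Kaplan-Meier tends to 43.75% × 2^(−(6/7)(t − 24)/12).
- Month 36: 24.2% against a true 23.4%. Month 48: 13.3% against 12.1%.
- At month 36, of 30 subjects, 30 × 0.2344 = 7.0 are alive. Those at risk number 30 × 2^(−12/6) × 0.4375 = 3.3.

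**Wider range (simulation).** Four models were run over assumed medians of 3–9 months on treatment and 6–24 months after, 20 scenarios in all. Three of the models allow 10% of subjects to die on treatment. The error is Kaplan-Meier minus truth, in percentage points:

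| Model | Month 24 | Month 36 | Month 48 |
|---|---|---|---|
| Constant hazard after stopping | 0.0 | 0.0 to +0.8 | 0.0 to +2.0 |
| Prognosis shared by both phases | 0.0 | +1.2 to +2.0 | +2.5 to +5.0 |
| Hazard falls with time since stopping | 0.0 | −1.5 to −0.4 | −3.8 to −1.5 |
| Stopping unrelated to death | 0.0 | about 0 | −0.2 to +0.2 |

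With 30 subjects the standard deviation of the month-36 estimate was 8 to 10.5 points in the three scenarios checked. Expected numbers at risk at month 36 ran from 0.1 to 11 of 30. A median beyond month 24 can shift either way: in the longest-survival scenarios it was 46.7 against a true 41.0 months with shared prognosis, and 42.2 against 43.2 with a falling hazard.

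The deaths-only mean and the mean of observed times were below the true mean in all 20 scenarios. Under constant hazard the deaths-only mean ranged from 10.6 against 12.1 months to 21.6 against 44.2.

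**The case against.** The strongest defence is that little in the plan depends on the tail. The one Kaplan-Meier statistic named for OS is the median, which is exact if it falls before month 24, as in the base case. SAP 5 disclaims formal hypothesis testing, the sample size rests on clinical judgment, and no decision rule uses OS. The link from treatment stop to prognosis is also loose. Treatment may stop for toxicity, intercurrent illness or withdrawn consent, and Protocol 7.15.6 lets some patients continue beyond progression. All of this stands, and it is why the tail is the minor part of the point.

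A reader might infer that the tail, and the average with it, is biased upward in the drug's favour. The documents do not support that. The tail error is upward if early stoppers who are still alive have worse later survival than those still observed. It is about zero if stopping is unrelated to death, and downward if the death hazard falls with time since stopping. The documents give nothing with which to choose among these. For the average, both literal readings err downward. Only a Kaplan-Meier mean carried past month 24 could err upward, by at most 0.5 months at a 48-month horizon in these models, and no such mean is planned.

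It can also be said that the word average loosely means the Kaplan-Meier median. That is possible, but no text says so, and the formula and default statistics point to an arithmetic mean.

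**Conclusion.** The point holds in two parts of unequal weight.

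1. **Average survival time.** It is undefined. Under the SAP's formula and default statistic it understates mean survival: 18.0 or 21.6 months against 26.0 in the base case. The shortfall depends on the assumed durations. Its sign did not change in any scenario, because subjects alive at the end of follow-up are either dropped or counted only up to their last contact.
2. **Kaplan-Meier OS beyond month 24.** Censoring is potentially informative and the direction is unknown. The error ran from −1.5 to +2.0 points at month 36 across the assumed models, small beside a sampling standard deviation of 8 to 10.5 points.

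The rule does not affect OS to month 24 or a median below it. That assumes the planned contacts take place. Loss to follow-up, withdrawn consent or the one-month visit window could end observation a little or a lot sooner. This is a low-severity point, worth correcting because the plan as written can produce a wrong headline number.

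**What to change.** In SAP 2.7.1, 7.10.7 and 8.2.1.5:

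- Censor subjects not known to have died at the date last known alive.
- Replace the average survival time with the Kaplan-Meier restricted mean to 24 months from first dose, and state that this is how the same phrase in Protocol 8.7.3 is to be read. It uses only the part of the curve that the follow-up rule leaves intact. In the base case it is 2 × 17.31 × 0.75 − 8.66 × 0.9375 = 17.9 months lived out of the first 24. Its closeness to the deaths-only 18.0 is a coincidence of these inputs; the two measure different things.
- Report OS at 12 and 24 months.
- Keep the full Kaplan-Meier curve and the median, and show numbers at risk. Label estimates beyond month 24 as descriptive, because the remaining risk set is limited to longer-treated subjects.

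Censoring every OS analysis at month 24 is not needed. It would discard later observed deaths and make a median above 24 months inestimable.

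The cost is SAP wording only, with no new data, and SAP 12 describes the document as a first draft. The downside is that the reported mean describes only the first 24 months.
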